5.10.3 Criteria and Survey for Eligibility

Enrollment criteria for hospitals include a) being a licensed acute care U.S. hospital belonging to Hospital Corporation of America, and b) willingness to be randomized at the hospital-level to either usual bathing care or decolonization. Within hospitals, units that were eligible for participation included a) participating adult units of the following types: adult step-down (transitional care after leaving an ICU), medical, surgical, medical/surgical, and oncology non-critical care units, b) minimal current use of routine daily chlorhexidine bathing in these units (<30% of patients), c) less than 30% of unit patients undergoing cardiac or

arthroplastic surgery, and d) average length of stay of at least 2 days. Among eligible units, we will allow for national standards for pre-operative bathing with chlorhexidine and pre-operative *S. aureus* decolonization for cardiac and arthroplastic surgery. In addition, hospitals must confirm that they will avoid other discretionary infection prevention and quality initiatives for the duration of the trial, both the 1-year baseline and 18-month intervention period, (NOTE: intervention was extended to a 21-month trial in June 2015). The baseline period begins in the planning year and extends into the first half of the UH3 trial phase. Further details of the trial design, including rationale for the baseline observation period and timeline are found in UH3 Aim 3, Section 6.10.4.

We will exclude pediatric and specialty units, including psychiatry, obstetrics/post-partum, bone marrow transplant, and rehabilitation/skilled nursing units. Adult units that occasionally have children <12 are permissible, but children <12 admitted to participating units will not be included in the mupirocin protocol.

For each potential hospital participant, enrollment criteria will be assessed by administering an electronic survey to each eligible unit's champion as well as through the evaluation of baseline administrative data from the HCA data warehouse. The survey will additionally request contact information and details about infection prevention practices, bathing practices, and use of chlorhexidine and mupirocin. As done previously, surveys will be administered through HCA's usual survey channels and results will be compiled and returned to investigators in a database format. An example survey from our previous REDUCE MRSA trial is provided in **Appendix A**.

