5.40.2 Hospital Corporation of America Centralized Data Warehouse

The following data elements (Table 4) will be requested from HCA’s Information Technology team to sample patient descriptors and baseline primary outcomes and ensure adequate processes for high quality data pulls. For details about trial design, outcomes, and analysis, see UH3 Aim 1 (Section 6.10).

Table 4. Data Elements Requested from HCA’s Centralized Data Warehouse

Source Data	Desired Results	Elements
Primary Outcome		
Census Data	Adult patient days by unit Readmissions within 30 days	Patient identifier (coded), hospital, unit location, hospital and unit admission date, hospital and unit discharge date, age in years, gender
Microbiology Finalized Results	Sterile site cultures, all pathogens	Pathogen name (if culture is positive), patient identifier (coded), date of collection, body site of collection, antimicrobial susceptibility, quantification of urine culture count (e.g. >50,000 colonies)
Claims data	Identification of infectious readmissions	Diagnosis codes (ICD9) Procedure codes (ICD9/CPT codes)
Descriptors		
Claims data	Identification of comorbidities Use as case mix adjustors	Diagnosis codes (ICD9)
Pharmacy	Mupirocin dispensing	Patient identifier (coded), date range dispensed, unit location
Supply Chain	Chlorhexidine use	Patient identifier (coded), date used, unit location

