6.10.2 Preliminary Data – Results of REDUCE MRSA Trial of Decolonization in ICUs

The REDUCE MRSA Trial was an 18-month 3-arm cluster-randomized trial involving 74 adult ICUs in 43 community hospitals,²⁰⁵ with the goals of reducing clinical isolates of MRSA and bloodstream infections due to all pathogens. All ICUs in a hospital were assigned to the same arm. Study arms were: 1) **screening and isolation (pre-trial standard of care)**: nasal screening for MRSA followed by isolation if positive, 2) **targeted decolonization**: screening, followed, if positive, by isolation and decolonization with chlorhexidine baths and nasal mupirocin for 5 days, and 3) **universal decolonization**: cessation of screening, universal application of mupirocin for 5 days, and daily chlorhexidine baths. Proportional hazards models with shared frailty were used to assess differences in infection reductions across the arms while accounting for clustering by hospital.

We randomized 43 hospitals in 16 states. There were 74 adult ICUs with 48,390 admissions in the baseline period and 74,256 in the intervention period. There were significant differences between arms in the relative hazards for intervention vs. baseline for both clinical isolates of MRSA and bloodstream infections caused by all pathogens (Table). In each case, universal decolonization produced a significantly greater reduction than screening and isolation. Targeted decolonization was not significantly different from screening and isolation alone. Adjusted analyses yielded similar results (Table).

Table. Primary Outcome Event Rates and Proportional Hazard Model Results for REDUCE MRSA Trial

Strategy	ICU-Attributed MRSA Clinical Cultures				ICU-Attributed Bloodstream Infections (all pathogens)			
	Baseline*	Intervention*	HR [^]	HR _{adj} ⁺	Baseline*	Intervention*	HR [^]	HR _{adj} ⁺
Screening and Isolation	13.7	11.9	0.92	1.0	16.8	15.3	0.99	0.98
Targeted Decolonization	16.1	12.2	0.75	0.83	17.9	13.8	0.78	0.77
Universal Decolonization	13.8	8.3	0.63	0.69	23.7	13.7	0.56	0.55
P-value [§]	--	--	0.01	0.02			<0.0001	<0.0001

* Events per 1,000 patients

[^] HR = Hazard Ratio from primary unadjusted analysis; model estimates are not equal to ratio of raw risk due to differential length-of-stay and effect of clustering within hospital

⁺ HR_{adj} = Hazard Ratio from secondary adjusted analysis

[§] P-value from proportional hazards model

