HCA hospitals will be randomized into two study arms. Both arms will continue to conduct routine MRSA screening for high risk patients and will place MRSA+ patients in isolation precautions. The first arm will continue the routine policy of offering assisted or unassisted daily showers/bed baths with regular soap, and will agree not to institute components of the other arm for the duration of the study. In the second arm, all patients will be encouraged to shower or have a bed bath daily with chlorhexidine products. In addition, patients known to be MRSA+ will receive nasal mupirocin ointment twice a day for 5 days. We anticipate an average of 4 adult non-critical care units per hospital, for a total of 200+ units across the 54 hospitals.

For full recruitment details, see UH2 Aim 1. Participating hospitals will commit to having all eligible general adult non-critical care units participate in the trial. These are defined as step-down, medical, surgical, medical/surgical, and oncology units. Children <12 admitted to participating units will not receive the mupirocin protocol.

Hospital leadership will identify a trial champion for each unit as well as a liaison from their Infection Prevention Program and their Microbiology Laboratory. Participants agree to report all new initiatives slated to occur during the trial and to defer them if study investigators determine that they conflict with the trial. In addition, participating hospitals agree to collect bacterial isolates as specified in UH3 Aim 2 (Section 6.20).

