6.10.11 Statistical Analysis

All outcomes will be assessed similarly. Here, we use the example of the primary outcome: clinical cultures with MRSA or VRE (first per patient). MRSA and VRE clinical cultures will be attributed to participating units if the collection date occurred >2 days after admission to that unit through two days after discharge from that unit. This attribution is consistent with CDC guidance for surveillance of nosocomial infections.²⁰⁸

Main trial results will be based upon as-randomized, unadjusted analyses using proportional hazards models to account for patients' variable tenure in the unit. This is necessary for the usual reasons: dichotomizing patients into those with vs. without infections would require us to define a fixed time-frame (within first x days of eligibility, ignoring some infections and omitting patients with shorter stays) or to ignore exposed time (counting infection during unit stay regardless of different length of stay). In addition, power is greater for proportional hazards models than for logistic regression models.^{209 210 211 212}

As discussed with the Statistical Core Working Group of the Collaboratory, clustering within hospital will be accounted for using shared frailties. The frailties are added model terms that allow unique hazards ratios for each hospital, and are necessary to account for clustered randomization.²¹³ Model terms will include individual-level data on arm, hospital, outcome events, trial period (baseline vs. intervention) and an interaction term between trial period and arm. The assessment of trial success will be determined by the significance of the interaction term, which assesses whether the difference in hazard between the baseline and intervention period differs significantly between the two arms. We can write a simple version of the model symbolically as:

$$\lambda_{ij}(t) = \lambda_0(t)e^{\beta_1 Arm_{ij} + \beta_2 Period_{ij} + \beta_3 Arm_{ij} * Period_{ij} + \gamma_i}$$

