where i is a hospital, j is a person within the hospital, Arm and $Period$ are indicator variables and are = 0 for patients in a hospital in the control arm or baseline period and 1 if in the intervention arm or period. The overall hazard rate over time for person ij is defined as $\lambda_{ij}(t)$, a function of the baseline hazard $\lambda_0(t)$, which is similar to the intercept in a linear model, times the proportionality for that subject, which is defined by the covariates Arm_{ij} and $Period_{ij}$ and the associated parameters, as well as the frailty, γ_i . The frailties are closely analogous to the random effect in generalized linear mixed models, and account for the clustering (similarity of hazard) within a given hospital. The ultimate effect of the intervention is assessed through β_3 : as parameterized, if it is negative and has p-value < .05 (or 95% CI excluding 0) then the intervention reduces the risk of infection. We plan to assess the need for different frailties by hospital by period (instead of just by hospital), as well as additional clustering by unit within hospital. In addition, we will investigate the need to adjust for the stratified randomization scheme described above in **Section 6.10.53**

Subsequent analyses will include as-treated and covariate-adjusted models. Adjusted models will account for individual characteristics such as age, gender, comorbidities based upon ICD-9 codes, and receipt of intervention products. We will also account for unit type (step down, medical, surgical, etc.) and baseline bathing frequency if this is not balanced after randomization. All analyses will be performed using current versions of SAS (9.4, as of writing, SAS Institute, Cary NC) and/or R (3.0.2, as of writing).²¹⁴

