6.10.13 Limitations and Planned Solutions

This study has limitations. First, we require the enrollment of at least 50 HCA hospitals. While we believe this is possible due to our previous trial of 43 HCA hospitals, should enrollment drop unexpectedly to less than 50, we will pursue an elongation of the 18-month trial, (NOTE: intervention was extended to a 21-month trial in June 2015). Secondly, if hospital committee approvals for trial protocols are delayed, we will expand the phase-in period to a total of 3 months. We note that our prior trial completed phase-in within 30 days. Third, if decolonization is significantly better at preventing infection, we appreciate that we are unlikely to be able to distinguish between effects of chlorhexidine and the effects of active encouragement to bathe or shower. Nevertheless, the results of this study would reflect a real world intervention which would likely entail both processes.

Cluster randomization does not allow every question of interest to be addressed. It typically results in more misclassification of exposure than individual randomized controlled trials do, either because individual providers choose to use a non-recommended regimen for some patients, or they fail to adhere fully to the assigned regimen. To the extent that the frequency of failure is consistent with the level that occurs in usual clinical practice, these failures are part of the overall effectiveness measure. Thus, cluster randomization in inpatient systems may offer a relatively low-cost and broadly generalizable means to examine many of the priority topics for comparative effectiveness research. In addition, this study design does not allow for blinded assignment or implementation. Nevertheless, this reflects the pragmatic nature of our intervention and directly mirrors the design and implementation of hospital quality improvement initiatives.

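### The secondary adjusted models condition on product receipt, which the assigned arm produces, so their hazard ratio is not a case-mix-corrected as-randomised effect

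*Protocol*

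**What the plan says.** Protocol 6.10.11 and SAP 2.2 carry the same text on this point. The primary result is safe: "Main trial results will be based upon as-randomized, unadjusted analyses", with success judged on the arm-by-period interaction (beta3). Two further kinds of model are then announced, as-treated and covariate-adjusted. The next sentence reads: "Adjusted models will account for individual characteristics such as age, gender, comorbidities based upon ICD-9 codes, and receipt of intervention products". Unit type is added, and baseline bathing frequency if it is unbalanced.

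The products in question are the assigned treatment. Under Protocol 6.10.4, every patient in the decolonization arm is encouraged to bathe or shower daily with chlorhexidine, and "patients known to be MRSA+ will receive nasal mupirocin ointment twice a day for 5 days". The usual-care arm undertakes not to adopt these components.

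Table 4 (Protocol 5.40.2) marks only the claims diagnoses as case-mix adjusters. Product data sit in separate pharmacy and supply-chain rows; the chlorhexidine row asks for "Patient identifier (coded), date used, unit location". Neither document says how receipt would be coded, describes an adjusted model without it, or says how the adjusted hazard ratio will be presented.

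**The concern.** Age, gender and pre-existing comorbidity are fixed before treatment. Receipt is not. Some of it is unrelated to arm: use in the baseline period, permitted pre-operative use, and the under-30% routine chlorhexidine bathing that Protocol 5.10.3 tolerates. In the intervention period, however, the difference in receipt between arms exists because of the assignment. Holding receipt constant therefore strips from beta3 whatever acts through the patient's own treatment with the product that is coded. What remains is a residual: less spread between patients (Protocol 1.9), the effect of a product that is not coded, or the encouragement component, which Protocol 6.10.13 says the trial is "unlikely to be able to distinguish between effects of chlorhexidine and the effects of active encouragement to bathe or shower".

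Even that residual reading needs receipt to be unrelated to risk, given the other covariates. This is doubtful. Protocol 5.30.3 lists refusal by the patient or the physician among the reasons for no chlorhexidine, and mupirocin goes to known MRSA carriers, while MRSA cultures are part of the primary outcome.

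Receipt adjustment also takes out non-adherence. Protocol 6.10.13 says of adherence failures at the usual-practice level that "these failures are part of the overall effectiveness measure".

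At stake is how the secondary result is read. The group's earlier ICU trial tabulated unadjusted and adjusted hazard ratios together and reported that "Adjusted analyses yielded similar results" (Protocol 6.10.2). If the same is done here, a gap between the two could reflect conditioning on receipt, case mix, or both. Agreement between them would not be reassurance either.

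**Working it through.** The plan has no figure to reproduce here, because the point is one of model specification. The only number taken from it is the 20% effect (Protocol 6.10.12, SAP 2.3), read as an interaction hazard ratio (HR) of 0.80. The other inputs are assumptions. The 29% and 5–12% values are set by limits or ranges in the documents.

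**Set-up.** Four equal arm-by-period cells, 0.5% event risk, constant hazards, Poisson maximum likelihood on expected counts (no simulation error). Two fits are compared:

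- without receipt: log rate = a + b1·Arm + b2·Period + b3·Arm·Period
- with receipt: the same + c·Receipt

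Let p be the proportion receiving chlorhexidine in the decolonization arm during the intervention, q the proportion in the other three cells, and s the share of the log effect *not* carried by own receipt. The receipt HR θ is set so that the total effect is 0.80:

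(1 − p + pθ) / (1 − q + qθ) = 0.80^(1−s)

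Example: p = 0.80, q = 0.29, s = 0 gives θ = 0.648, since (0.20 + 0.80 × 0.648) / (0.71 + 0.29 × 0.648) = 0.718 / 0.898 = 0.80.

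**Step 1: receipt unrelated to risk** (p = 60, 80, 90%; q = 5, 15, 29%). Without receipt, exp(b3) = 0.800. With receipt, exp(b3) = 0.80^s in all nine settings:

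- s = 0: 0.80^0 = 1.000
- s = 0.25: 0.80^0.25 = 0.946
- s = 0.5: 0.80^0.5 = 0.894

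**Step 2: check with hospitals.** 54 simulated hospitals, hospital fixed effects in place of the planned frailties, 150 runs per setting, s = 0, p = 60–90%, q = 2–29%. Without receipt, the HR was 0.79–0.81 and 89–97% of runs were significant for benefit. With receipt, it was 0.99–1.01 and 1–3% were.

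**Step 3: selective receipt.** One fifth of patients differ in risk and are bathed less; overall uptake is 80% (0.2 × 60% + 0.8 × 85%, or 0.2 × 40% + 0.8 × 90%). Cells give exp(b3) with receipt, for s = 0 / s = 0.5. The last two columns give background receipt the same odds ratio between risk groups.

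| Group bathed less | q = 5% | q = 15% | q = 29% | q = 5%, selective | q = 29%, selective |
|---|---|---|---|---|---|
| Hazard ×2, uptake 60% v 85% | 1.102 / 0.974 | 1.061 / 0.937 | 1.045 / 0.922 | 1.137 / 1.013 | 1.090 / 0.971 |
| Hazard ×3, uptake 40% v 90% | 1.382 / 1.195 | 1.236 / 1.055 | 1.183 / 1.002 | 1.470 / 1.297 | 1.295 / 1.138 |
| Hazard ×0.5, uptake 40% v 90% | 0.878 / 0.798 | 0.928 / 0.843 | 0.947 / 0.861 | 0.851 / 0.769 | 0.908 / 0.819 |

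When higher-risk patients are bathed less, receipt looks more protective than it is, so the adjustment overcorrects and b3 rises. When lower-risk patients are bathed less, b3 falls.

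**Step 4: mupirocin receipt also coded.** Known carriers 5, 10 or 12% (range taken from carriers at discharge, Protocol 1.6), hazard ×3, ×5 or ×10; 80% of carriers treated in the decolonization arm during the intervention and 2, 5 or 10% elsewhere; mupirocin HR 1.0, 0.8 or 0.5. Chlorhexidine receipt is unrelated to risk (p = 80%; q = 5, 15, 29%), s = 0, 0.25 or 0.5. Keeping settings with a chlorhexidine HR of at most 1, exp(b3) runs from 0.557 to 0.939. With mupirocin coded alone it runs from 0.504 to 0.788. Receipt now marks high-risk carriers, mainly in one cell, which pushes b3 down.

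**The case against.** The strongest reply is that the sentence follows one naming both as-treated and adjusted models, opens its list with a phrase that leaves it open, and is the only place where covariates for either kind are given. Receipt may have been meant to define the as-treated model. That is possible, but the text assigns receipt to the adjusted models. If the intent was otherwise, it is in the wrong sentence and the same edit is needed.

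Second, the documents never call the adjusted HR a case-mix-corrected effect, and Protocol 6.10.2 does not say which covariates the earlier trial used. Both are true. The harm depends on how the result is presented, which the plan leaves open. The non-adherence statement in Protocol 6.10.13 is also honoured by the primary analysis.

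Third, the sizes rest on assumptions. In Step 3 the selection is treated as wholly unmeasured, whereas age, gender, comorbidity and unit type would absorb some of it. The carrier range in Step 4 is for discharge, not for known carriers on participating units. These points stand: the ranges show that the shift can go either way; they do not predict its value. Step 1 does not depend on uptake.

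Fourth, deletion also drops background use that the assignment did not cause, such as permitted pre-operative chlorhexidine. This is so, but a patient-level receipt variable cannot separate that use from assigned use. A hospital-level measure of use before assignment would not share the problem, but it is not what the sentence lists.

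**Conclusion.** The concern holds. As written, the covariate-adjusted models condition on a consequence of assignment, and their beta3 cannot be read as the as-randomised effect corrected for case mix. With a true HR of 0.80 and receipt unrelated to risk, the adjusted HR is 0.80^s, that is 1.00, 0.95 or 0.89 when all, three quarters or half of the log effect runs through own receipt. With selective chlorhexidine receipt the illustrations span 0.77 to 1.47, and with mupirocin also coded 0.56 to 0.94. The net direction is therefore not predictable. These sizes assume the uptake, risk ratios and pathway shares listed above; the structural point does not depend on them. The consequence is confined to secondary models, so this is a correction that should be made rather than a threat to the trial's main conclusion.

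**What to change.** In Protocol 6.10.11 and SAP 2.2, delete the last item (product receipt) from the list of adjusters. Limit the patient and unit covariates of the adjusted models to age, gender, pre-existing comorbidity, unit type, and baseline bathing frequency if unbalanced. The separate question of adjusting for the randomisation strata stays open as now.

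Use receipt only in the as-treated analysis and state its coding there. The dated chlorhexidine and mupirocin data already requested in Table 4 would allow, for example, a time-varying exposure.

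The core edit is one phrase in one sentence of each document, plus a line on as-treated coding. Data collection and the primary analysis do not change.

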6.10.12 Power (Updated June 2015, following reassessment of power)

In many settings, an analytic approach to power is possible: given the assumptions of the model (e.g., logistic regression) are met, a relatively simple closed-form solution exists. However, generating the expected values to plug in may be difficult. In addition, some settings are complex enough that closed-form solutions may be difficult to generate. Many cluster-randomized designs fall into this class. In cluster-randomized problems, it is also difficult to obtain reliable estimates of the additional parameters that are required, most notably the between-cluster variance or, equivalently, the intra-class correlation coefficient. Further additional complications are introduced for time-to-event outcomes such as those needed in the ABATE Infection Trial.

In a previous trial, we used the logistic regression analogue to proportional hazards regression models and simulation to estimate power.²¹⁰ Now, however, we propose an interesting and, to our knowledge, novel approach to power calculation, which we dub “bootstrap power calculation.” This method is described below and in an article published since the trial was planned.²¹⁵ Briefly, the bootstrap is a powerful technique that uses the observed sample to approximate the underlying population, rather than a convenient analytic distribution.²¹⁶ The bootstrap power approach relies on the fact that we possess a large quantity of baseline data already. Loosely put, we (1) bootstrap a sample of observations from our observed baseline data to serve as the baseline sample in the power calculations. Then we (2) bootstrap another sample from the baseline data to serve as the intervention period data. Next, (3) we implement the randomization scheme in the bootstrapped sample. Then (4), for a randomly selected subset of the outcomes (e.g., bloodstream infections) observed in the bootstrapped intervention period sample in the hospitals randomized to intervention, we artificially change the outcome from infection to no infection. This represents the effect of the intervention, which we control by changing the size of the subset selected for this change. Simultaneously (5), for this subset we change the date of the event from the date of infection to the date of discharge, transfer to a non-eligible unit, or death—i.e., the date of censoring, had no infection been observed. Finally (6), we fit the planned frailty model described in **Section 6.10.11** above and record whether the null hypothesis of no association was rejected or not. This process is repeated many times, and the proportion of rejections is an estimate of the power under the given effect size. A confidence limit on this estimated power can be generated. In the table below, we show the power for removing the outcome from 0, 10, 20, and 30% of the subjects in the intervention arm in the intervention period. Removing 0% of the outcomes is a test of the technique: since we are not reducing the infection rate, the null is true, and rejections should occur only about 5% of the time.

In the initial planning of the trial, we used the available 4-month baseline sample of patients from our participating trial hospitals and used three bootstrap samples to represent each 12-month baseline and 4.5 bootstrap samples to represent the 18-month intervention period. This resulted in the power shown in **Table 13**.

Table 13: Power and Exact 95% CI for Primary and Select Secondary Outcomes*

Intervention Effect	Primary Outcome MRSA, VRE Clinical Cultures	Gram Negative MDRO** Clinical Cultures	All Pathogen Bacteremia
*0%	5.6% (4.3-7.2%)	4.1% (3.0 – 5.5%)	5.2% (3.9 – 6.8%)
10%	33% (28-37%)	15% (12 – 18%)	23% (19 - 27%)
20%	92% (90-94%)	44% (40 – 49%)	68% (63 - 72%)
30%	100% (99-100%)	82% (79 – 86%)	98% (96 – 99%)

*Based on 500 bootstrap samples for each effect size, except for the 0% estimate, for which we did 1000 simulations to increase confidence that the alpha level is maintained when the null is true.

** Gram-negative multi-drug resistant organism clinical cultures

The above power estimates (**Table 13**) show that the technique has the desirable characteristic of rejecting the null only 5% of the time when it is true. We also see that power for MRSA or VRE clinical culture is ample, even if we prevent only 20% of the infections. For both selected secondary outcomes, the power is less, but still quite acceptable if the intervention prevents 30% of the infections. The primary strengths of the bootstrap power approach are that it allows us to avoid using literature estimates for the parameters when such estimates may not apply to the trial population, and it also avoids unrealistic assumptions about regularity (equal cluster sizes) or distribution (logistic instead of frailty models). The main weakness in this case is that correlation within hospital is generated to be the same in the baseline and intervention periods. In addition, we have not received all desired randomization stratification data by the time of this submission. Thus, stratification in the bootstrap process is limited to hospital size and the baseline rate of the outcomes. We believe that these are relatively benign issues: the correlation structure is unlikely to change importantly from

period to period during the actual study, and the stratification is mainly to promote balance. It may affect the power, but mainly by reducing the variability in the outcome.

After the baseline period, we were able to re-estimate the power, using the data collected in the full baseline period. We used the bootstrap process outlined above, except that we used the observed 12-month data for the baseline. We assessed the power for the original proposal of an 18-month intervention and for a slightly extended 21-month intervention period, oversampling the observed 12-month baseline data as needed in each case (see Table 14). This updated power assessment was considered to be more accurate in that it used approximately three times as much real data—12 months vs. four months—compared to the original estimate. Furthermore, additional cleaning steps were applied to the 12 months of baseline data. In these new assessments we focused on an intervention effect of 20%. The power for the primary outcome was 99.9% (95% CI: 99.4-99.99%) with 18 or 21 months of follow-up. For all pathogen bacteremia, the power was 85% (95% CI: 83-87%) with 18 months follow-up and 89% (87-90%) with 21 months follow-up. The steering committee decided to use 21 months of follow up to ensure greater power with less common secondary outcomes and account for lessened effects at sites that may drop out of the trial.

Table 14: Revised Power and Exact 95% CI for Primary and Select Secondary Outcomes*

Analysis	Effect	Primary Outcome MRSA, VRE Clinical Cultures	All Pathogen Bacteremia
As-randomized, 18-mo	20%	99.9% (99.4% – 99.99%)	85% (83% – 87%)
As-randomized, 21-mo	20%	99.9% (99.4% – 99.99%)	89% (87% – 90%)

